11 STUDY PROCEDURES

11.1 VISIT SCHEDULE

Subjects will be assessed during a total of up to 10 visits during the study, as detailed in the following sections (see also Study Schedule of Assessments).

11.2 STUDY EVALUATIONS/PROCEDURES

11.2.1 Screening Period – Collectively named Visit 1 – from Day -7 to Day -1

The screening visit can be performed within Day -7 and Day -1 before randomization and screening activities will comprise the following:

- 1. Obtain written informed consent, signed and dated by the subject, after the nature of the study has been explained and before any study procedure is performed.
- 2. Demographic data: age, gender, ethnicity.
- 3. Record of relevant medical and surgical history including subject's history of CIPO, number of pseudo-obstruction episodes and in the previous 6 months.

4.	Assessment of responder status	(e.g.,
) according to investiga	tor's judgement and medical history (subjects who
	have history of benefit	or never treated (naïve)
	and subjects non responders).

5. Record of relevant medication history:

	 all medications (i.e., prescription and over-the-counter medications, herbals, vitamins, and supplements) used within 30 days of the screening visit to be recorded. (Attention will be paid to prohibited treatments)
-	Subject's history of within 30 days of the screening visit will also be recorded including the name of medication, date started and stopped,
	route of administration, indication, dose and reason for stopping, to be recorded in the e-CRF. Last intake (e.g.,
), if previously taken by the subject, should be recorded as previous medication, even if taken more than 30 days before the screening visit.
6. 7.	
	apid swab virus testing (to be performed on the same day of and results to be a fore starting
 Biometric m calculated. 	neasures: weight in kilograms, height in centimeters, body mass index (BMI) to be
11.	
12. 13. Blood collec	ction (in fasting condition):
-	
14.	
	e Breath Test (L-BT). diary and instruct the subject on how to complete the electronic diary (e-diary), which
encompass	
before rand	These questionnaires should be completed by the subject on Day -1, omization and then weekly afterwards.

17. Verify inclusion and exclusion criteria.

daily throughout the study duration.

18. Record any adverse events occurred since signing the ICF.

In addition, subjects will be instructed on how to record

19. Schedule Randomization visit (V2, if eligible).

of the day before randomization (Day -1) and

11.2.2 Visit 2 (Randomization Visit- V2)

The following procedures will be performed at the randomization visit:

Pre-Randomization:

- 1. 2.
- 3. 4.
- 5. Review and record any AEs that occurred since the previous visit.
- 6. Review and record any concomitant medications taken since the previous visit (attention will be paid to prohibited treatments).
- 7. Re-instruct the subject on how to complete the electronic diary (e-diary), which encompasses the
- 8. e-diary review for eligibility according to inclusion **criterium n 4**. Questionnaires will be completed at the clinical center before randomization if not already completed by the subject.
- 9. Confirmation of inclusion and exclusion criteria.
- 10. completion by the subject.
- 11. Randomization (if still eligible).
- 12. Blood collection (in fasting condition) sample (30 mins prior to drug administration) for proof for absorption.
- 13. Treatment dispensing (if subject has been randomized).

Dosing:

First investigational product dose will be administered under the supervision of the study personnel in the morning, on an empty stomach, with water. Time of dosing will be registered.

After the investigational product administration, the following procedures will be completed:

Post-dose:

- 14. 15. 16.
- 17. Retrain the subject on how to use the electronic diary (e-diary), instructing to complete:
 - The subject will be instructed to record, starting from Day 1, investigational
- product intake information daily.

 18. Schodulo port visit and remind the subject to not to take the investigational product in the
- 18. Schedule next visit and remind the subject to not to take the investigational product in the morning of the next visit, but to take the bottle to the clinic.

11.2.3 Visit 3 (V3; Day 28±1)

The following procedures will be performed at V3:

- 2. 3.
- 4.
- 5. 6.
- 7. Blood collection (in fasting condition):

- 11. Review and record any concomitant medications taken since the previous visit (attention will be paid to prohibited treatments).
- 12. 13.
- 14.
- 15. Review and record any AEs that occurred since the previous visit.
- 16. Review the e-diary to assess the completeness and retrain the subject as needed.
- 17.

Dosing:

Investigational product dose will be administered under the supervision of the study personnel in the morning, on an empty stomach, with water. Time of dosing will be registered.

After the investigational product administration, the following procedures will be completed:

Post-dose:

- 18. 19.
- 20. Blood samples for analysis for proof of absorption:
- 21. Collect all investigational product bottles and account investigational product.
- 22. Schedule next visit.

11.2.4 Start of Treatment (SOT) Visits: Visit 4 (V4, Day 43 ± 1), Visit 6 (V6, Day 85 ± 1) and Visit 8 (V8, Day 127 ± 1)

The following procedures/assessments will be completed at V4, V6 and V8:

Pre-dose

1.

5.

2. 3. 4.

6. Blood collection (in fasting condition):

- 13. Review and record any AEs that occurred since the previous visit.
- 14. Review the e-diary to assess the completeness and retrain the subject as needed. Questionnaires not yet completed should be completed by the subject at the clinical center before investigational product administration
- 15.
- 16. Dispense investigational product.

Dosing:

Investigational product dose will be administered under the supervision of the study personnel, in the morning, on an empty stomach, with water. Time of dosing will be registered. After the investigational product administration, the following procedures will be completed:

[figure not shown]
Post-dose:

- 17.
- 18. Schedule next visit and remind the subject not to take the investigational product in the morning of the next visit, but to bring the bottle to the clinic, if the visit is scheduled at the clinical center; If the subject cannot go back to the clinical center for the next visit (EOT period), a home visit will be scheduled for the subject.
- 11.2.5 End of Treatment (EOT) Visits: Visit 5 (V5, Day 70 ± 1), Visit 7 (V7, Day 112 ± 1) and Visit 9 (V9, Day 154 ± 1)

The following procedures/assessments will be completed at V5, V7 and V9, if the subject can attend the visit at the clinical center:

Pre-dose

- 1. 2.
- 3.

- 13. Review and record any AEs that occurred since the previous visit.
- 14. Review the e-diary to assess the completeness and retrain the subject as needed.
- 15.

Dosing:

The last dose of the investigational product period will be administered under the supervision of the study personnel, in the morning, on an empty stomach, with water. Time of dosing will be registered.

After the investigational product administration, the following procedures will be completed:

Post-dose:

- 16.
- 17. Collect all investigational product bottles and account investigational product.
- 18. Schedule next visit.

Home visit: In case the subject cannot attend the visit at the clinical center, this visit can be scheduled at the subject's home and a home nursing service will perform the visit. The clinical staff at the study center may attend the visit remotely. The data collected (source documents) during the home visits by the nurse will be transmitted on the same day to the clinical center in order to allow the study doctor to perform a preliminary clinical evaluation regarding safety. In case of home visits the subject will take the investigational product about 2 hours before the nurse's visit in the morning and the same procedures scheduled for the visit at the clinical center will be performed with the exception of physical examination that will not be performed.

The nurse will collect the empty packs and the unused investigational product of the relevant period during Visit 5, Visit 7 and Visit 9

11.2.6 End of Follow-up (EFU; Day 169 ±1)

The following procedures/assessments will be completed during End of Follow up Visit, if the subject can attend the visit at the clinical center:

- 1. 2.
 - CONFIDENTIAL

6. Blood collection (in fasting condition):

- 12. Review and record any AEs that occurred since the previous visit.
- 13. Review the e-diary to assess the completeness.

Home visit: In case the subject cannot attend the visit at the clinical center, this visit can be scheduled at home and a home nursing service will perform the visit. The clinical staff at the study center may attend the visit remotely. The data collected (source documents) during the home visits by the nurse will be transmitted on the same day to the clinical center in order to allow the study doctor to perform a preliminary clinical evaluation regarding safety. In case of home visits, the same procedures scheduled for the visit at the clinical center will be performed with the exception of physical examination that will not be performed.

11.2.7 Early Termination Visit (ETV)

The following procedures/assessments will be completed during the ETV. if the subject agrees to perform the visit and can attend the visit at the clinical center:

6. Blood collection (in fasting condition):

- 13. Review and record any AEs that occurred since the previous visit.
- 14.
- 15. Review the e-diary to assess the completeness. Weekly questionnaires will be completed during the ETV.
- 16. Collect all investigational product bottles and account investigational product.

Home visit: In case the subject cannot attend the visit at the clinical center, this visit can be scheduled at home and a home nursing service will perform the visit. The clinical staff at the study center may attend the visit remotely. The data collected (source documents) during the home visits by the nurse will be transmitted on the same day to the clinical center in order to allow the study doctor to perform a preliminary clinical evaluation regarding safety. In case of home visit the same procedures scheduled for the visit at the clinical center will be performed with the exception of physical examination that will not be performed.

The nurse will collect the empty packs and the unused investigational product of the relevant period during the ETV.

11.2.8 Early Switch Visit (ESV; anytime between Day 1 and Day 126)

The following procedures/assessments will be completed in case of ESV occurrence (see section 6 Overall Study Design and Plan): The ESV will be considered as Day 1 of SOT-2 or SOT-4, as appropriate.

Pre-dose

- 1. 2. 3. 4. 5.
- Blood collection (in fasting condition):

- 13. Review and record any AEs that occurred since the previous visit.
- 14. Review the e-diary to assess the completeness and retrain the subject as needed. Weekly questionnaire will be completed during this visit. Questionnaires not yet completed should be completed by the subject at the clinical center before investigational product administration
- 15.
- 16. Collect all investigational product bottles and account investigational product (if applicable).
- 17. Dispense investigational product.

Dosing:

Investigational product dose will be administered under the supervision of the study personnel, in the morning, on an empty stomach, with water. Time of dosing will be registered. After the investigational product administration, the following procedures will be completed:

Post-dose:

- 18.
- 19. Schedule next visit and remind the subject not to take the investigational product in the morning of the next visit, but to bring the bottle to the clinic, if the visit is scheduled at the clinical center; If the subject cannot go back to the clinical center for the next visit (EOT), a home visit will be scheduled for the subject.

After this visit, the subsequent visits will follow the relevant sequential number (see Study Schedule of Assessments).

11.2.9 Contingency activities in case of travel restrictions due to SArS-COV2 pandemic

In case the subject or the nurse cannot travel to attend/perform any of the scheduled visit due to travel restrictions due to sanitary emergency, the clinical site will implement all the procedures able to maintain the subject in the study, always taking in primary consideration the safety of the subject. Tele-medicine visits could be implemented in order to collect as much as possible information, as foreseen by the specific study schedule, and if the case will organize the investigational product delivery at the subject's home, throughout a dedicated courier able to trace the transportation and guarantee the appropriate transport condition.

11.3 LABORATORY TESTS

During the study period, it can be estimated that a total volume of up to approximately 300 ml of blood will be drawn for each subject.

Additional safety laboratory tests may be performed, as required for extra study assessments.

will be performed locally, and results assessed locally at the clinical center or samples will be sent to Bologna, Italy for analysis and result assessment.

Handling of Biological Samples

Blood and urine samples for hematology, clinical chemistry, and urinalysis collected during the home visits will be handled according to a centralized laboratory procedure.

Blood and urine samples for hematology, chemical chemistry, and urinalysis collected during the visits performed at the clinical center will be handled according to the local clinical laboratory procedures.

Plasma samples for proof of absorption will be stored at -20°C/-80°C before shipment to the bioanalytical laboratory. Additional details on the collection, processing, storage and shipment of these samples can be found in a "Proof of absorption sample handling laboratory manual".

Samples are shipped within qualified shippers (these range from Ambient to dry ice) that meet and maintain the storage temperature for the samples whilst in transit.

11.4 SUBJECT DIARY

Diary data will be collected and reviewed throughout the course of the study electronically until the end of the follow up period (2-weeks after last dose). The subjects will collect weekly information regarding

Investigational product intake and time will be recorded daily during the treatment periods.

daily during all the study duration (4-week treatment periods, 2-week wash out periods and 2-week follow up period).

This e-diary is integrated in the electronic data capture system utilized for the collection of all the other study data. The clinical site staff will review periodically the e-diary data collected and in case of missing data will be responsible for reminding the subject about appropriate completion. The diary data collected during the different study periods will be also revised by the clinicians in occasion of each scheduled study visit.

11.5 UNBLINDING OF RANDOMIZATION IN CASE OF EMERGENCY

In accordance with the double-blind design, both the Investigator and the subject will be unaware of the treatment actually being dispensed in each case. The overall randomization code will be broken at the study end. This will occur once Blind Data Review Meeting has been held and clinical database has been locked.

During the study, the blind should be maintained for persons responsible for the ongoing conduct of the study (such as management, Monitors, Investigators).

ONLY the PV-Clinical Safety of the Sponsor may unblind, and ONLY for safety reasons upon Clinical Safety Manager and EU-QPPV decision or for regulatory purposes (when SUSAR has to be submitted as expedited to RAs and ECs).

The PV-Clinical Safety of the Sponsor can break the blind using the online tool embedded in the e-CRF system.

The Investigator, ONLY in the case of an emergency safety issue, can unblind a subject's treatment assignment, when knowledge of the study medication is essential for the clinical management or welfare of the subject. Most often, investigational treatment discontinuation and knowledge of the possible treatment assignments are sufficient to treat a study subject who presents with an emergency condition. The investigator will inform the subject how to contact their backup in cases of emergency when he/she is unavailable. Should a situation arise where unblinding is required, the investigator at that site may perform immediate unblinding without the need for communication with the Sponsor.

As a rule, the Investigator can break the blind using the online tool embedded in the e-CRF system.

Page 59/94

However, in case of system malfunction, the Investigator can at any time open the specific treatment envelope assigned to the subject.

After the emergency blind-breaking, the Investigator must notify the unblind, as soon as possible, to the Sponsor Clinical Safety Manager without sharing the treatment information to other people involved in the study (see contact details in section 15 Safety Aspects).

The investigator must record the date and time the blind was broken and the reason that treatment assignment information was required.

The blind should be maintained for persons responsible for the ongoing conduct of the study (such as sponsor and CRO representatives, monitors, sub-investigators); if not the subject must be withdrawn from the study and procedures accompanying withdrawal are to be performed.

In cases where there are ethical reasons for the subject to remain in the study, the Investigator must obtain specific approval from the Sponsor for the subject to continue in the study.

12 EFFICACY AND SAFETY ASSESSMENT

12.1 ASSESSMENT OF EFFICACY

12.1 ASSESSMENT OF EFF	FICACT	
During the present study	y the assessment of the efficacy of velusetrag versus placebo will be	based
on collection of the		sing a
subject's e-diary as d esc	cribed below.	
In addition,	will be	
	dy, according to the Stu dy Schedule of Assessments in order to asse	ss the
treatment impact on subj	oject's nutritional status.	
	_	
The	will be evaluated at the screening visit as well as at the end of the t	first 4-

12.1.1 Primary Efficacy Parameters

The primary efficacy parameter will be the change in weekly global gastrointestinal symptoms average index score from start to the end of each treatment period.

week treatment period in order to assess the investigational product impact on

The weekly global gastrointestinal symptoms average index score is obtained by averaging the scores for each of the 4 symptoms assessed weekly: abdominal pain, bloating, nausea and vomiting.

Symptom severity will be graded 0 – 4 according to its influence on subjects' usual activity, as previously described (Barbara, 2004) (0 – Absent; 1 - Mild (not influencing usual activities); 2 - Moderate (diverting from, but not urging modification of, usual activities); 3 - Severe (influencing usual activities markedly enough to urge modifications; 4 - Extremely severe (precluding daily activities).

Predominant symptoms of CIPO include nausea and vomiting, associated with weight loss, when the functional derangement primarily affects the upper gastrointestinal tract, while diffuse abdominal pain, abdominal distension and constipation are suggestive of a more distal involvement of the gut (Antonucci, 2008)

In order to assess the efficacy of velusetrag on major gastrointestinal CIPO symptoms, subjects will be asked to score severity of their symptoms: abdominal pain, bloating, nausea and vomiting over the last week (Appendix 2).

Subjects will complete the gastrointestinal symptom severity questionnaire, including 4 questions, to assess the following symptoms of CIPO: abdominal pain, bloating, nausea and vomiting during the study, starting on day -1 and then weekly during each treatment period and wash out period and

during the 2-week follow up period. Gastrointestinal symptom severity questionnaire will be also completed in case of ETV or ESV.

12.1.2 Secondary Efficacy Parameters

1		

12.3 APPROPRIATENESS OF MEASUREMENTS

Not Applicable

13 PHARMACODYNAMIC ENDPOINTS

13.1 DESCRIPTION AND TIME POINTS/INTERVALS FOR MEASURING THE PHARMACODYNAMIC ENDPOINT(S)
Not Applicable

14 PHARMACOKINETIC ENDPOINTS

Not Applicable

[figure not shown]
14.1 BLOOD SAMPLING FOR PROOF OF ABSORPTION

14.1 DE001	O AMILIE TO TOTAL TROOP OF ALBOORI HOR	
		_
		_
		_

Actual collection time will be recorded for each blood collection. Blood samples for plasma concentration analysis of velusetrag and the active metabolite, THRX-830449, will be collected, processed and stored at the study site and shipped for analysis at a bioanalytical laboratory.

Blood will be drawn using an indwelling intravenous cannula inserted into a forearm vein.

The blood sample will be collected with a 4-mL vacutainer (K2EDTA). The dead space of the cannula will be flushed using a small amount of sterile saline following each blood sample to ensure cannula patency. Prior to withdrawal of blood sample, 2 mL of fluid will be drawn and discarded.

Study code: VE-CIP2001/2021 Final ve

15 SAFETY ASPECTS

15.1 ADVERSE EVENTS

15.1.1 Definition of Adverse Events

An AE is any untoward medical occurrence in a patient or clinical trial patient administered a medicinal product which does not necessarily have a causal relationship with this treatment. An AE can therefore be any unfavorable and unintended sign (including an abnormal laboratory finding), symptom, or disease temporally associated with the use of an investigational product, whether or not related to the investigational product.

For recording purpose, the Investigator must consider that:

An AE does include any:

- Symptoms associated with disease not previously reported by the patient.
- Exacerbation of pre-existing illness.
- Increase in frequency or intensity of a pre-existing episodic event or condition.
- Condition detected or diagnosed after investigational product administration even though it may have been present prior to the start of the study.
- Continuous persistent disease or symptoms present at baseline that worsen following the start of the study,

An AE does not include a/an:

- Medical or surgical procedure (e.g., surgery, endoscopy, tooth extraction, transfusion); the event that leads to the procedure is an AE.
- Planned medical or surgical procedures.
- Pre-existing diseases or conditions present or detected at the start of the study and that do not worsen during the study.
- Situations (e.g., hospitalization for cosmetic elective surgery, social and/or convenience admissions); where an untoward medical occurrence has not occurred.
- Signs, symptom and/or altered laboratory values identified as study endpoints, unless more severe than expected for the patient's condition.
- Symptoms often associated with the disease under study (other than those mentioned above) that are consistent with the patient usual clinical course unless the symptom(s) meet(s) the criteria for "serious".
- Overdose of concurrent medications without signs or symptoms.

Observations matching an adverse event after ICF is signed but occurring when the study medication is not administered (during the screening/washout/follow-up period), by definition represent AEs, and should be recorded as such. In the report these observations will be described separately.

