5 STUDY OBJECTIVES AND ENDPOINTS

5.1 PRIMARY STUDY OBJECTIVE AND ENDPOINT

Primary Study Objective	Primary Study Endpoint					
To investigate the efficacy of velusetrag in improving the symptoms severity associated with CIPO, in subjects with idiopathic CIPO and CIPO	Change in weekly global gastrointestinal symptoms average index score* from start to the end of each treatment period.					
secondary to neurodegenerative or demyelinating conditions (e.g., Parkinsonian Syndromes, multiple sclerosis etc.).	*The weekly global gastrointestinal symptoms average index score is obtained by averaging the scores for each of the 4 symptoms assessed weekly: abdominal pain, bloating, nausea and vomiting.					
	Rating of symptoms (i.e. abdominal pain, bloating, nausea and vomiting) is using a recall period of 7 days and a Likert scale with the following categories:					
	0 – Absent					
	1 - Mild (not influencing usual activities)					
	2 - Moderate (diverting from, but not urging modification of, usual activities)					
	3 - Severe (influencing usual activities markedly enough to urge modifications)					
	4 - Extremely severe (precluding daily activities)					

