15.1.2 Definition of Serious Adverse Events

A SAE is any untoward medical occurrence in a patient or clinical trial patient administered a medicinal product which does not necessarily have a causal relationship with this treatment. A SAE can therefore be any unfavorable and unintended sign (including an abnormal laboratory finding), symptom, or disease temporally associated with the use of an investigational product, whether or not related to the investigational product and resulting in:

- Death.
- Life-threatening.
- In-patient hospitalization or prolongation of existing hospitalization.
- Persistent or significant disability/incapacity.
- Congenital anomaly/birth defect.

Other event(s) considered important medical event.

Examples of other events which could be considered medically important and reported as serious are: intensive treatment in an emergency room or at home for allergic bronchospasm; blood dyscrasias or convulsions that do not result in hospitalization; or development of drug dependency or drug abuse.

Clarifications:

- "Occurring at any dose" does not imply that the patient is receiving investigational product.
- Life-threatening means that the patient was, in the view of the Investigator, at immediate
 risk of death from the event as it occurred. This definition does not include an event that,
 had it occurred in a more severe form, might have caused death.
- Hospitalization for elective treatment of a pre-existing condition that did not worsen during the study is not considered an SAE.
- Complications that occur during hospitalization are AEs. If a complication prolongs hospitalization, the event is a SAE.
- "In-patient" hospitalization means the patient has been formally admitted to a hospital for medical reasons. This may or may not be overnight. It does not include presentation at a casualty or emergency room.
- With regard to important medical events, medical and scientific judgement should be used in deciding whether prompt reporting is appropriate in this situation.

An unexpected adverse event is an AE whose nature, severity or outcome is not consistent with the information given into the reference document as defined in the study protocol.

Expected serious adverse reactions should be considered always unexpected if:

- ➤ have an unexpected outcome (e.g., a fatal outcome).
- > have an increase in the rate of occurrence, which is judged to be clinically important.

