15.1.8 Prompt Reporting of SAE to the Sponsor

Any serious adverse event occurring during the study, once the Investigator determines that the event(s) meet the protocol definition of a SAE, regardless whether related or not to the investigational drug, must be reported immediately (i.e. within 24 hours) to the Sponsor (or its designee).

Information about all SAEs will be reported using the SAE tool of the eCRF. In case of technical difficulties, SAE notification can be carried out filling paper SAE Report form and it must be mailed or faxed using the following contact details:

One "SAE Report form" should be used for each SAE. However, if at the time of initial reporting, multiple SAEs are present that are temporally and/or clinically related, they may be reported on the same "SAE form" preferably as a diagnosis.

The SAE form must be written in easily readable reading way. It must be completed as thoroughly as possible with all available details of the event, signed by the Investigator (or appropriately qualified designee), and reported immediately to the Sponsor (within 24 hours from first awareness of the event).

If the Investigator does not have all information regarding the event, he/she will not wait to receive additional information before compiling the form and notifying the event to the Sponsor, although the following minimal information is required:

The following minimal information is required as initial report:

- Name, affiliation, telephone and fax number of the reporting Investigator
- Investigational product(s)
- Study code
- Study Centre number
- Patient identification number, sex and age (years)
- Last investigational drug administration
- Description of the adverse event,
- Measures taken if any
- Causal relationship by the investigator

The Investigator will always provide his/her assessment of causality at the time of the initial report.

The additional information as soon as available will be recorded in a separate SAE form completed in every part that will be sent as a follow-up report.

If follow-up information obtained subsequently leads the investigator to change the assessment of causality, the SAE form may be appropriately amended, signed and dated, and resubmitted to the Sponsor as follow up report.

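### Protocol 15.1.1 gives endpoint symptoms no seriousness exception, which conflicts with its own inclusion list and with 15.1.2 and 15.1.8, so a hospital admission for such a symptom may be reported at one site and not at another

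*Protocol*

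**What the plan says.** Protocol 15.1.1 gives investigators two lists to apply when recording events.

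The list of what an adverse event does not include has two bullets on disease symptoms:

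- The first covers endpoints: "Signs, symptom and/or altered laboratory values identified as study endpoints, unless more severe than expected" for the patient's condition.
- The second covers symptoms commonly seen in the disease, limited to those "other than those mentioned above) that are consistent with the patient usual clinical course unless the symptom(s) meet(s) the criteria for" serious.

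The list of what an adverse event does include contains "Exacerbation of pre-existing illness" and "Continuous persistent disease or symptoms present at baseline that worsen following the start of the study". It also names a rise in the frequency or intensity of an episodic condition that the patient already had.

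The primary endpoint score (Protocol 5.1) is "obtained by averaging the scores for each of the 4 symptoms assessed weekly: abdominal pain, bloating, nausea and vomiting".

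Section 15.1.2 opens its SAE definition with the same general sentence that opens the adverse event definition, without the two lists, and then names outcomes. One of them is "In-patient hospitalization or prolongation of existing hospitalization". Its only exemption for an admission concerns elective treatment of an existing condition that has not worsened.

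Section 15.1.8 requires a report within 24 hours, "once the Investigator determines that the event(s) meet the protocol definition of a SAE".

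SAP 6.4.3 tabulates treatment-emergent adverse events by actual treatment. Each event is attributed to the last treatment taken before it began.

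**The concern.** The four endpoint symptoms are central symptoms of the disease, and two of them are also ways in which harm from the drug could appear. Protocol section 4 names nausea and abdominal pain among the expected adverse events of the drug class. Section 8 asks for monitoring of exaggerated gastrointestinal responses, especially when treatment starts. Section 4 also says, when discussing intravenous erythromycin, that patients with acute exacerbations are usually admitted. An admission for vomiting or pain is therefore a realistic event in this trial.

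If such an event is not recorded as an adverse event, it cannot enter the SAP 6.4.3 tables. If it is also not handled as an SAE, it misses the 24-hour report and the assessment that follows from it. No data monitoring committee is planned (Protocol 16.4.1 and 18.4). The steering committee's safety role in 18.3 is to raise repeated issues, which supposes that events have been recorded. With 16 subjects, a single event handled differently at two sites would be visible in the safety comparison.

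**Working it through.** The plan states no figure on this point, so the check compares the texts. Take one event: a subject has an unplanned in-patient admission for vomiting, and the investigator regards its severity as expected for that patient.

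1. **Endpoint bullet of 15.1.1.** Vomiting is one of the four endpoint symptoms (5.1). It was not more severe than expected. Under this bullet the event is not an adverse event. Seriousness is not among the bullet's exceptions.

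2. **Next bullet of 15.1.1.** This bullet has a seriousness exception, but it sets aside the symptoms of the bullet before it. The exception does not reach vomiting.

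3. **Inclusion list of 15.1.1.** If the vomiting is an exacerbation, or is worse than at baseline, the event is an adverse event. Steps 1 and 3 then disagree, and the section does not say which list prevails. Severity expected for the patient's condition and worsening since the start of the study are different tests, so one event can satisfy both.

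4. **15.1.2.** The SAE definition does not say that the event must first pass the lists of 15.1.1. The event led to an in-patient admission that was not elective. Read on its own, 15.1.2 makes it an SAE.

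5. **15.1.8.** The 24-hour duty begins when the investigator decides that the SAE definition is met. An investigator who goes from step 4 to step 5 reports the event. One who stopped at step 1 may never make that decision.

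Two other places make stopping at step 1 plausible. Inclusion criterion 4 (Protocol 9.2) requires at least two of the four symptoms at score 3 or higher, so severe symptoms are part of the entry picture. The early-switch text in section 6 foresees an exacerbation that permitted medication does not control and that is nevertheless not judged an adverse event. The protocol thus already expects sites to class some exacerbations as non-events.

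**Size.** If all 16 subjects complete, there are 16 × 4 = 64 treatment periods, each with its following two weeks off drug, and 32 of them are velusetrag periods. The documents give no admission rate. Purely as an illustration, assume that 2%, 5% or 10% of periods include an admission for an endpoint symptom:

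| Assumed rate | All periods (64 × rate) | Velusetrag periods (32 × rate) |
|---|---|---|
| 2% | 1.28 | 0.64 |
| 5% | 3.2 | 1.6 |
| 10% | 6.4 | 3.2 |

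These are admissions to which the conflicting texts could apply. They do not count lost reports. If every site follows 15.1.2 and 15.1.8, the number lost is zero.

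**The case against.** A reader might infer that the protocol prescribes non-reporting: the event is not an adverse event, hence not an SAE, hence not reportable. The documents do not support that. Section 15.1.2 defines an SAE in its own terms and 15.1.8 refers to that definition. Read literally, an unplanned admission for an endpoint symptom is reportable. The inclusion list of 15.1.1 also means that unexpected severity is not the only way for such a symptom to count. A subject newly admitted for pain or vomiting would often have worsened since baseline. The comparator in the endpoint bullet is the individual patient's condition, so it cannot be assumed that every severe symptom would be called expected.

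Further, the contents list a section 15.1.3 on expected and protocol-specified SAEs. Its text is not in the available copy. That is not a gap in the plan, and the section may settle the matter.

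All of this stands, and it limits the conclusion. It does not remove the conflict. The available text does not say whether the exclusions of 15.1.1 also bind 15.1.2. The wording supports some doubt: if 15.1.2 always caught serious events regardless of 15.1.1, the seriousness exception for other disease symptoms would not be needed for SAE reporting. Its presence in one bullet and absence from the other can be read as deliberate. Depending on which section it opens first, a site could reach either answer in good faith.

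**Conclusion.** The point holds as an inconsistency. The endpoint bullet of 15.1.1 conflicts with the inclusion list of the same section and with 15.1.2 and 15.1.8. The result is a risk that a serious event involving abdominal pain, bloating, nausea or vomiting is recorded and reported at one site and left out at another.

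The size cannot be determined from the documents. It depends on how often such admissions occur, how often their severity is judged expected, and which section a site applies first, and none of these is given. The conclusion rests on the available text and is conditional on 15.1.3. It does not show that any event would certainly escape SAE reporting, and it does not show that the serious events affected would be caused by the drug. Section 4 lists nausea and abdominal pain as expected events of the class, not as serious ones.

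The point is worth acting on because it bears on subject safety, there is no data monitoring committee, and the correction is small.

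**What to change.** This is a cheap improvement. In Protocol 15.1.1, extend the exception at the end of the endpoint bullet. The exclusion should lapse when the sign, symptom or laboratory value is more severe than expected for that patient, or when it meets any seriousness criterion in 15.1.2. Check the new wording against 15.1.3 so that the two agree.

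The next bullet can stay as it is. Removing its limitation to non-endpoint symptoms is unnecessary and would place endpoint symptoms under two overlapping bullets with different tests.

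The added phrase makes a serious endpoint symptom an adverse event and an SAE under every section, reportable under 15.1.8 and included in the SAP 6.4.3 tables if it is treatment-emergent. It changes reporting only. The cost is one phrase in the protocol, a reminder to the sites and a few more SAE forms.
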